## **2.7. Timing of Outcome and Covariate Assessments**

Participating households were followed from enrollment until the index child reaches (or would have reached, assuming a live birth and continued vitality) their first birthday. For the purposes of this analysis plan, severe pneumonia follow-up is through the first year of life.

HAP exposure was assessed prenatally and postnatally. The measurement periods were 24 hours. Prenatal exposures include one measurement at baseline (<20 weeks, denoted as the BL measurement in our trial) and two post-randomization (at 24-28 weeks' gestation denoted as P1; and at 32-36 weeks' gestation denoted as P2). We measured child postnatal exposures indirectly as a reconstructed average of maternal personal exposures and two area concentrations three times at ages 3 (denoted as the B1 measurement), 6 (denoted as B2) and at 12 months (denoted as B4). A validation subset of 10% of participants had double the numbers of measures, with extra measures at time points spaced between those of the main study.

Time-invariant covariates that are potential confounders and effect modifiers were collected at baseline and birth. If effects of time-varying exposures are considered, covariates that could be time-varying confounders were collected at quarterly household visits during infancy (e.g. vaccination, breast feeding).

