### 5.1 Overview of Key Analysis Variables for Manuscript

Personal HAP exposures were measured directly in pregnant women/mothers both prenatally and postnatally, including fine particulate matter (PM2.5), black carbon (BC), and carbon monoxide (CO). Postnatally, we measured area concentrations in the kitchen and infant's bedroom. Personal exposures to PM2.5 and CO in infants will be assessed indirectly. Specifically, we will use logging transponders on the mother and in the kitchen and bedroom, and the infant will wear emitters. We have developed and validated an interpolation algorithm to estimate indirect exposures in infants; however, we will consider different approaches to estimate personal exposure in infants if missingness of emitter/transponder logging data is ≥10%. We summarize HAP exposures in the trial in Table 1. Per protocol, exposure variables used in exposure-response models were calculated as weighted averages of subsets of these assessments (Section 6.1). However, we also explore performance of alternative predictions of longer-term exposure using our exposure validation sub-study.

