As for post-natal values of  $X_{ij}$ , we will consider two approaches for measuring averages. The first will use means of values for  $\mathbf{X}$  for the  $j^{th}$  quarter using all values of personal exposures to  $PM_{2.5}$  that fall in the first quarter defined in Table 4, or the average of any prior exposures thereafter. We will consider unweighted means of the  $PM_{2.5}$  (or CO) exposures, and weighted mean of the values for  $\mathbf{X}$  considering the distances in time between the ages when personal exposures to  $PM_{2.5}$  were measured and the age at the start of the  $j^{th}$  quarter. The third approach uses a regression model to estimate infant's mean personal exposures. As children's data are missing for about 50% of post-natal measurements, we will use the mother's personal exposure measured at the same timepoint when the infant's measurement is missing. The unadjusted correlation of maternal and infant measurements is about 0.89. Prior work has shown that when using a regression model to predict time-specific infant exposures using mother's post-natal exposure and adjusted for season, weekend, and IRC, has correlation of 0.95 when compared with the infant's observed personal exposure. Using the assumption that maternal and child personal exposures measurements are similar, we anticipate that we will only have ~10% missing child exposure data. We will select the best approach for modeling exposure from the approach that leads to the least amount error in estimation of exposure (based on a root mean squared error in validation study).

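### The correlations of 0.89 and 0.95 behind the maternal fill-in are measured against an infant value built partly from the mother's own monitor, and the fill-in leaves out the kitchen and bedroom readings scheduled at the same visits

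*SAP*

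**What the plan says.** **The fill-in (SAP 6.1).** The rule starts from the statement "As children's data are missing for about 50% of post-natal measurements" and puts the mother's same-timepoint reading in the gap. Two figures support it: an unadjusted maternal-infant correlation of about 0.89, and an earlier regression on the mother's exposure with season, weekend and IRC, whose prediction "has correlation of 0.95 when compared with the infant's observed personal exposure". The paragraph continues "Using the assumption that maternal and child personal exposures measurements are similar" and expects only about 10% of child exposure data to stay missing.

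**How the infant value arises.** Section 2.7 states: "We measured child postnatal exposures indirectly as a reconstructed average of maternal personal exposures and two area concentrations three times". Section 5.1 describes the location system: "we will use logging transponders on the mother and in the kitchen and bedroom, and the infant will wear emitters". It also says "Postnatally, we measured area concentrations in the kitchen and infant's bedroom". Table 1 labels the infant column as an indirect measurement. It schedules kitchen and bedroom PM2.5 and CO at B1, B2 and B4, the same visits as the maternal reading.

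**Choosing among exposure approaches.** Section 6.1 picks the approach with the smallest RMSE in the validation study, without naming the reference value. Section 2.7 describes that subset as 10% of participants with twice as many measures, the extra ones falling between the main visits.

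**The concern.** Section 6.1 calls observed what sections 2.7 and 5.1 call reconstructed. The mother's reading is one of three inputs to that reconstruction, so each correlation compares a reading, or a prediction from it, with a quantity that contains it, including the same monitor's error on the same day. Such a part-whole correlation does not tell the reader how well the mother's reading represents what the infant breathed. Nor does any correlation address level: a maternal reading always twice the infant's would correlate at 1.00, yet section 6.1 substitutes the raw maternal value.

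The second issue is the choice of fill-in. The missing quantity is a weighted average of three monitors. The stated rule uses one of them, and the cited regression adds only season, weekend and IRC. The other two inputs are scheduled at the same visits.

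At stake is the post-natal exposure in the primary model. A large share of it rests on this substitution, and section 5.2 already expects error in indirect exposure to depend on arm, which one pooled correlation cannot show.

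**Working it through.** **1. Is the mother's reading on both sides?**

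| Place | Infant post-natal value |
|---|---|
| SAP 2.7 | Average reconstructed from the maternal reading and two area readings |
| SAP 5.1 | Assessed indirectly; emitters on the infant, loggers on the mother and in kitchen and bedroom |
| SAP Table 1 | Indirect measurement, PM2.5 and CO only |
| SAP 6.1 | Described as observed, and used as comparator for 0.89 and 0.95 |

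The overlap is therefore explicit for both figures.

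**2. Share of values affected.** Of 100 post-natal measurements, about 50 lack an infant value and about 10 stay missing after filling. So 50 − 10 = 40 are maternal substitutes among 100 − 10 = 90 usable values: 40/90 = 44%. This reads both percentages as shares of the same set of measurements.

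**3. Can the plan's 0.89 and 0.95 be reproduced?** No. They are empirical, and the SAP gives no variances, location shares or correlations between monitors. A range under assumptions is all that is possible. Let M, K and B be the maternal, kitchen and bedroom readings, with SD 1 for M and s for K and B, a common pairwise correlation ρ, and infant value I = wM + ((1−w)/2)(K + B). Then

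corr(M, I) = [w + (1−w)ρs] / √[w² + (1−w)²s²(1+ρ)/2 + 2w(1−w)ρs].

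Results with s = 1 (w, ρ and s are all assumed):

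| ρ | w = 0.2 | w = 1/3 | w = 0.5 | w = 0.6 | w = 0.7 | w giving 0.89 |
|---|---|---|---|---|---|---|
| 0 | 0.333 | 0.577 | 0.816 | 0.905 | 0.957 | 0.58 |
| 0.3 | 0.592 | 0.730 | 0.867 | 0.923 | 0.962 | 0.54 |
| 0.5 | 0.728 | 0.816 | 0.905 | 0.943 | 0.970 | 0.47 |
| 0.7 | 0.845 | 0.894 | 0.943 | 0.965 | 0.981 | 0.32 |

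With area SD twice the maternal SD (s = 2), 0.89 needs w = 0.73, 0.70, 0.64 and 0.49 for the same four values of ρ.

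Two things follow. A shared component can produce a correlation of 0.89 without separate evidence about the infant. It need not do so: low maternal weights give much lower values. The formula covers the unadjusted 0.89 only. The 0.95 belongs to a regression prediction with further terms, which this model does not represent.

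**4. Which monitors enter the fill-in?**

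| Quantity | Mother | Kitchen | Bedroom | Other terms |
|---|---|---|---|---|
| Reconstructed infant value (2.7) | yes | yes | yes | location data |
| Stated substitution (6.1) | yes | no | no | none |
| Cited regression (6.1) | yes | no | no | season, weekend, IRC |

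**The case against.** The strongest reply has four parts.

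- **The weight carries information.** A high correlation does not follow from the construction alone; it needs a substantial maternal weight. That weight comes from emitter data, so a large one would partly mean that the infant really was near the mother. This stands. It is why the size of any inflation cannot be stated and why the correlations should not be dismissed as artefact.
- **The comparison is the relevant one for imputation.** When the missing item is the reconstructed value, agreement with the reconstruction is a proper check of the fill-in. This stands for that narrow purpose. It does not reach accuracy for the infant's own exposure, nor similarity in level.
- **Area readings are used.** A reader might infer that the kitchen and bedroom data are wasted. The SAP does not support that: they enter every reconstructed infant value, section 6.1 does not list predictors for its own regression approach, and section 5.1 leaves unnamed alternatives open once location-data missingness reaches 10%. What stands is narrower: the stated substitution and the cited regression omit them.
- **The RMSE comparison may be sound.** A reader might infer that candidates are scored against the same-visit reconstruction, which would reward copying the mother's reading. The SAP does not say so. Section 5.1 links the validation sub-study to longer-term exposure, and section 2.7 places its extra measures between the main visits, which points the other way. Only the unnamed reference remains an issue.

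The SAP also does not say how often area readings exist when the infant value is missing; their availability is inferred from the schedule in Table 1.

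**Conclusion.** The point holds in a limited form. The figures 0.89 and 0.95 are agreement with a reconstruction that contains the mother's reading. They are not independent validation of the maternal proxy and say nothing about bias in level. About 44% of usable post-natal values would rest on the substitution, taking the SAP's 50% and 10% at face value. The amount of inflation cannot be computed from the SAP, and the range shown depends wholly on assumed weights, correlations and SDs.

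It would go too far to conclude that the correlations are worthless, that the maternal proxy is poor, or that the exposure-response estimate is biased by a known amount. The SAP feeds neither correlation into an error correction. The case for change is that a fuller prediction and a clearer description cost very little.

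**What to change.** 1. **Fill-in (SAP 6.1).** Where emitter data are missing but the monitors ran, replace raw maternal substitution with a prediction of the infant value from the mother's, kitchen and bedroom readings plus season, weekend and IRC, fitted in visits with a reconstructed value. Where an area monitor failed, fall back to the mother-only regression.
2. **Wording (SAP 6.1).** Call the infant value indirectly estimated, and describe 0.89 and 0.95 as agreement with a partly maternal reconstruction.
3. **RMSE reference (SAP 6.1).** State that RMSE in the validation subset is scored against measures from other visits, not against the same-visit reconstruction that contains the predictor. An other-visit value still has a maternal component, but not the same day's monitor error.

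Cost: SAP text and two predictors per pollutant that Table 1 already schedules; no new data collection. The downside is two prediction models and some missing area data. How much the area readings improve the prediction is not known from the SAP.

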**Table 4. Values of PM2.5 to use for exposure-response modeling.**

$t_{ij}$	Values for $X_{ij}$ (prenatal)*	Values for $X_{ij}$ (post-natal)
$t_{ij} \leq 3$		$X = \{PM_{2.5}(t = B1)\}$
$3 < t_{ij} \leq 6$		$X = \{PM_{2.5}(t = B1), PM_{2.5}(t = B2)\}$
$6 < t_{ij} \leq 12$	$X = \{PM_{2.5}(t = BL), PM_{2.5}(t = P1), PM_{2.5}(t = P2)\}$	$X = \{PM_{2.5}(t = B1), PM_{2.5}(t = B2), PM_{2.5}(t = B4)\}$

The error term for our regression model is a binomial distribution, and the canonical link is the logarithm function. Exponentiation of the difference between  $f(X_{ij})$  at different exposure values provides the risk ratio associated with that change in exposure. If we identify estimation problems when using the logarithm function, we will revert to use a logit function where exponentiation at different exposure values provides an odds ratio associated with that change in exposure. Since there are few cases (175 severe pneumonias) compared to the overall number of infant-quarters (~12,000), the odds ratio of a logistic regression should approximate the relative risk relatively well. We also do not expect zero-inflation to be a problem when using log or logit canonical links. The same log-linear (or logit) regression models will be used when using CO as the exposure, and in subgroup analyses and secondary outcomes, unless otherwise indicated.

*A priori* time-independent confounders will be crowding (number sleeping in house), IRC, SES, infant's sex and birthweight (or a z-score for birthweight for gestational age of child instead of birthweight). An SES score will be measured using a SES wealth index, but may also incorporate mother's education and nutrition data, and has been developed by our group and used in previous publications. *A priori* time-dependent confounders for the  $j^{\text{th}}$  quarter include age and season (winter or no), vaccination status, breastfeeding, and an indicator for pre vs post COVID-19 pandemic (i.e., 1 after March 15, 2020, and 0 otherwise).

As a secondary analysis we will conduct a time-to-event analysis using the Anderson-Gill method counting process method, which allows for repeated events for individuals. The start and stop times of the counting process will be defined according to the dates of exposure assessment for each child (i.e., birth to B1, B2 to B2, and B2 to B4), and the status will be classified as either pneumonia (where the outcome is 1) or no pneumonia (where the outcome is 0). Given that the underlying model based on Cox proportional hazards, we will test for proportionality of hazards assumption. To account for serial correlation of repeated time-to-event states for each child, we will use a sandwich estimator or random effects as defined by Amorim and Cai. The estimand for this model is a hazard ratio.

We will conduct subgroup analyses to identify potential effect modifiers: International Research Center (i.e., site), and known risk factors for severe infant pneumonia in LMICs (Table 5):

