## 5.2. Identification of Confounders

To assess conditions for identifiability of causal effects of HAP exposure on pneumonia, we gathered expert views on the causal relations among variables related to exposure, pneumonia, or the HAPIN study design. Confounder selection was based on conceptual directed acyclic graphs as shown in Appendix figures and code.

A key feature of this exposure-response analysis for causal inference is that it is conducted within the population of a randomized intervention trial that created a strong exposure contrast by arm. Nevertheless, HAP exposure is determined by many other factors and it is likely that some of these factors are common

causes of severe infant pneumonia or share a common cause with severe infant pneumonia. Since exposures are qualitatively and quantitatively different during gestational and postnatal periods, we have included a time-varying exposure that can take one value during pregnancy (HAP1\_T) and another after birth (HAP2\_T). The DAG can be analyzed for adjustment sets for estimating effects of prenatal exposure, postnatal exposure, or both of these exposures.

A general assumption in the DAG in appendix Figure 1 is that the HAPIN trial intervention can have direct effects on respiratory disease or effects that are not pathways going through HAP exposure. In particular, the provision of free fuel can have a large impact on the household economy and influence behaviors. For example, we have assumed the intervention has direct effects on breastfeeding, nutrition, healthcare seeking, maternal vaccination, and pneumonia. However, there was not a consensus in the research group about the pathway between intervention and severe pneumonia and the downside to conditioning on intervention could be reducing study power by reducing residual exposure variability (i.e.. greater variance of exposure-response estimates). The primary analysis will not condition on intervention or types of fuels and stoves.

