We also considered measurement error as a source of bias. The DAG includes nodes for measured (e.g. exposures HAP1\_M and HAP2\_M, and outcomes Pneumonia\_M) and true values of HAP exposure and severe pneumonia. These allow representation of structures that can be important for understanding information bias. For example, the HAPIN intervention can influence the probability that a caregiver with a sick child seeks care at a surveillance site or that the healthcare seeking event results in screening by HAPIN staff. Moreover, the spatiotemporal and dispersion properties of HAP would suggest that error in indirect exposure assessment is likely to be dependent on intervention arm and other determinants of exposure.

Based on our DAG, we have identified the following variables, for which we have data, as the minimal adjustment set to identify the effect of prenatal HAP exposure on severe infant pneumonia: crowding (number sleeping in house), intervention IRC, nutrition history of breastfeeding, SES, sex, birthweight, and a data for small for gestational age (z-score). As noted, intervention status will not be included for either pre or post-natal exposure as it will be superceded by measured exposure level.

Birthweight would need to be included to reduce bias for estimating effects of postnatal exposure, but conditioning on birth weight could bias estimates of prenatal exposure because it is suspected of being on the causal pathway, so caution must be exercised here.

We will conduct sensitivity analyses to assess variability between estimates with alternative sets of appropriate covariates. Confounders selected from adjustment sets are found in the HAPIN codebook.

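### Birth size is adjusted for in the prenatal model although the SAP itself suspects it lies on the causal pathway, and no prenatal model without it is named

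*SAP*

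**What the plan says.** Section 5.2 gives a list of covariates "as the minimal adjustment set to identify the effect of prenatal HAP exposure on severe infant pneumonia". The list includes "SES, sex, birthweight, and a data for small for gestational age (z-score"). The next paragraph separates the two exposure windows. For the postnatal effect it says "Birthweight would need to be included to reduce bias for estimating effects of postnatal exposure". For the prenatal effect it says "conditioning on birth weight could bias estimates of prenatal exposure because it is suspected of being on the causal pathway", and asks only for caution. It then adds: "We will conduct sensitivity analyses to assess variability between estimates with alternative sets of appropriate covariates". The sets are not named, and for the selected confounders the reader is sent to the HAPIN codebook.

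Section 6.1 makes both the prenatal and the postnatal relationship the main aim. It writes the linear predictor as a prenatal function plus a postnatal function, with one covariate vector taken from Section 5.2. The text after Table 4 lists the a priori time-independent confounders. Besides crowding, IRC and SES, these are the infant's "sex and birthweight (or a z-score for birthweight for gestational age of child instead of birthweight"). No exception is made for the prenatal term.

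**The concern.** A variable can be needed to identify an effect and also be a suspected source of bias for it only if the target is a particular kind of direct effect. The SAP does not say that it is. By the reasoning in Section 5.2 the two windows need different covariate sets, yet Section 6.1 gives them one.

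Mediation is not a remote possibility in this trial. Birth weight is one of its primary outcomes (Section 1.2), and aim 2 includes the exposure-response relationship for birthweight (Section 1.3).

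If birth size does mediate, the prenatal coefficient omits that part of the effect. If birth size and pneumonia also share an unmeasured cause, adjustment can shift the coefficient further. A reader who sees a weak prenatal estimate could not tell whether prenatal exposure matters little or acts largely through birth size. Section 6.1 carries the same models to CO, the subgroups and the secondary outcomes, so the ambiguity goes with them.

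**Working it through.** **Text comparison**

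- Section 5.2, covariate list: birthweight and the z-score are required for the prenatal effect.
- Section 5.2, next paragraph: birthweight is needed for the postnatal effect and may bias the prenatal one.
- Section 6.1: one list for both terms, with birthweight or its z-score. The z-score is also a measure of birth size, so choosing it does not remove the problem.
- Section 5.2 names both variables; Section 6.1 names one or the other and gives no rule for choosing.
- Neither section specifies a prenatal model without birth size.

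**Illustration of size**

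The SAP gives no association between exposure and birth size or between birth size and pneumonia. Only the 175 events come from it (Sections 5.1 and 6.1); every other input is assumed.

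*Removed pathway.* Let a be the fall in birth size (SD) per SD of prenatal exposure, and RR_bw the pneumonia risk ratio per SD lower birth size. Adjustment removes exp(a × ln RR_bw).

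*Precision.* With uncorrelated prenatal and postnatal exposure, the best-case SE of the log risk ratio per SD is 1/√175 = 0.0756. The half-width is 1.96 × 0.0756 = 0.148, so the 95% CI is the estimate times or divided by exp(0.148) = 1.16. If the two exposures correlate at 0.7, SE = 0.0756/√(1 − 0.49) = 0.1059, the half-width is 0.208 and the factor is 1.23.

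| Case | a | RR_bw | a × ln RR_bw | Removed RR | Share of half-width, correlation 0 | Share, correlation 0.7 |
|---|---|---|---|---|---|---|
| Low | 0.05 | 1.2 | 0.0091 | 1.009 | 6% | 4% |
| Middle | 0.2 | 1.4 | 0.0673 | 1.070 | 45% | 32% |
| High | 0.3 | 1.6 | 0.141 | 1.151 | 95% | 68% |

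*Unmeasured common cause U.* Let birth size = −aX + cU + e, with X, U and birth size scaled to variance 1, and let log risk rise by h per SD lower U. Adjusting for birth size then shifts the coefficient of X by −h × c × a/(1 − a²).

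| Case | a | c | h | Shift | Multiplier on RR |
|---|---|---|---|---|---|
| Low | 0.05 | 0.2 | ln 1.2 | −0.0018 | 0.998 |
| Middle | 0.2 | 0.3 | ln 1.4 | −0.021 | 0.979 |
| High | 0.3 | 0.5 | ln 1.6 | −0.0775 | 0.925 |

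A linear simulation of the high case (2,000,000 records, true direct effect 0.10) gave an adjusted coefficient of 0.0223. The formula gives 0.10 − 0.0775 = 0.0225.

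**The case against.** The SAP does not ignore the issue. Section 6.1 takes its covariates from Section 5.2, and so takes the warning with them. Section 5.2 says the DAG can be analysed for prenatal, postnatal or joint adjustment sets, and promises sensitivity analyses. It also states: "Confounders selected from adjustment sets are found in the HAPIN codebook". Section 6.2 says the replication team will receive a pre-specified covariate list. A set without birth size may therefore exist. This softens the point, but none of these places names such a set or says what the prenatal coefficient means. Section 6.2 also leaves alternative covariate specifications out of replication.

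Whether birth size belongs in a prenatal set depends on the DAG, whose figure cannot be seen in the copy reviewed. Removing birth size could open a confounding path. The primary analysis does not condition on arm, and Section 5.2 states: "we have assumed the intervention has direct effects on breastfeeding, nutrition, healthcare seeking, maternal vaccination, and pneumonia". If nutrition affects birth size, part of that path could be left open. This stands, and it is a reason to report both models rather than simply drop birth size.

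In the joint model the prenatal coefficient is already conditional on postnatal exposure, breastfeeding and vaccination, so dropping birth size alone does not give a total effect. Adjusting for birth size is also a recognised choice when two exposures are fitted together. This stands too, and the fix has to cover those variables.

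The magnitudes rest on unsourced inputs and run from negligible to material. They illustrate what could happen and do not show that the effect is large. The case for change rests on the text. The and/or mismatch between the sections is minor, since the wording in Section 5.2 is garbled; what remains is that Section 6.1 does not choose.

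**Conclusion.** The concern holds and should be fixed. Section 5.2 contradicts itself on birthweight for the prenatal effect. Section 6.1 then applies one list that includes birth size to both windows, without saying what the prenatal risk ratio represents. The textual conflict is certain.

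The numerical consequence is not known. Under the assumed inputs the removed pathway is a risk ratio of 1.01 to 1.15 per SD (middle case 1.07), and a shared unmeasured cause could multiply the adjusted estimate by a further 0.998 to 0.93. Even the largest removed pathway lies within the best-case confidence half-width. The effect measure itself is clear (risk ratio, with odds ratio as fallback). What is missing is whether it includes the pathway through birth size, and any named model without birth size.

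**What to change.** 1. State whether the prenatal target is the total effect or the effect not through birth size.
2. Reconcile the two paragraphs of Section 5.2. If the total effect is the target, take birthweight and the z-score out of the prenatal set.
3. Name in Section 6.1 a prenatal model without birthweight or its z-score, reported beside the adjusted model. Make it the main prenatal estimate if the total effect is the target. Otherwise make it a named sensitivity analysis, and state that the adjusted model assumes no unmeasured common cause of birth size and pneumonia. Say whether this model includes postnatal exposure, breastfeeding and vaccination, since these follow prenatal exposure and may also lie on the pathway.
4. Keep birth size in the model for the postnatal effect, and label the prenatal coefficient there as an effect not through birth size.
5. Fix in advance whether birth size enters as birthweight, the z-score or both, the same in Sections 5.2 and 6.1.

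The cost is SAP wording and one more model fit on existing data. The drawback is that the model without birth size may be confounded by causes of birthweight not otherwise adjusted for, and the SAP should say so.
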